******Protection against risks of alcohol challenges******

The alcohol challenges will be conducted by [name] and research staff, using methodology adopted from the Yale group, and trained by our Yale colleague, [name].

We provide a number of safeguards to reduce the risk of physical injury by supervising all sessions and having participants stay in the CRC until they are alert and do not show signs of psychomotor impairment. We also exclude participants for whom physical or psychological problems contraindicate alcohol consumption. By selecting non-treatment-seeking participants who are currently drinking heavily on a regular basis, we are not exposing participants to alcohol consumption levels that differ from their normal drinking context. Although this has not happened in the Yale group's experience, should a participant insist on leaving the research setting prematurely, we will provide transportation back to their residence. This contingency will be explicitly addressed in the consent form.

Clearly, participants are free to discontinue the experiment at any time, although we would strongly encourage them to remain in the research setting until their blood alcohol level is below .02 and alertness and psychomotor status are judged to be safe.

Because participants are not in treatment, participation in an alcohol challenge study will not interfere with efforts to achieve abstinence. At the end of the study, however, a potential benefit is that participants will be provided with a professional evaluation and treatment will be arranged if they express interest.

****Protection against the risk of heavier alcohol use, suicidality, or other medical or psychiatric problems that may arise over the course of the study****

To protect against this risk, we will do the following:

-We will closely monitor alcohol use at each visit.

-Participants will be withdrawn from the study if, in the opinion of the PI or the DSMB, there is: sustained clinically significant increase in alcohol use between ADP sessions 1 and 2, suicidal ideation consisting of suicidal intent or plan, unacceptable adverse events judged by the study physician (the PI, [name]) to be related to study interventions, or any other clinically significant medical, psychiatric, or substance use related poor outcome that makes continued study participation unsafe.

Blood and Urine Collections

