6.2.2.1 Adverse Events Definition and Reporting

Adverse Events

During the study, site personnel will note any change in the condition(s) and the occurrence and nature of any adverse events. Important clinical information that comes to light during study participation will be communicated by research coordinators to the study physician in real time.

The study physician (either the PI, [name]) will review each participant's safety at each study visit.

- Lab results will be reviewed on the same day that the results are received.
- Adverse effects reported by participants will be reviewed on the same day as they are reported by the study participant.
- Adverse effect assessment will be done by the research coordinators and discussed with the study physician on a daily basis, immediately after these adverse effects are reported by the participant to the study coordinator.

As with our current, CHR-approved clinical trials, the study physician, if not immediately present at the time of adverse effect data collection, will be contacted in real time by the study coordinator by phone, pager, or text message, so that adverse effects can be discussed with the study physician. The study physician, based on examination of the participant and/or review of the participant's data, will make a clinical judgment at each visit regarding whether it is safe to proceed with study medications.

The PI will report to the IRB, DSMB and study sponsor his assessment of the potential relatedness of each AE to protocol procedure, studied disease state, study drug via the CRF. For each adverse event recorded on the Adverse Event CRF, the PI will make an assessment of seriousness, severity, and causality.

According to the ICH guideline for Good Clinical Practice, an adverse event is any untoward medical occurrence in a clinical investigation participant administered a pharmaceutical product, regardless of causal attribution. An adverse event can therefore be any of the following:

- Any unfavorable and unintended sign (including an abnormal laboratory finding), symptom, or disease temporally associated with the use of a medicinal product, whether or not considered related to the medicinal product.
- Any new disease or exacerbation of an existing disease (a worsening in the character, frequency, or severity of a known condition).
- Recurrence of an intermittent medical condition (e.g., headache) not present at baseline.

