6.3 Study Procedures

6.3.1 Study Schedule

WEEK	STUDY VISIT	TIME PER VISIT^
Week 1	Screening visits	2.5 hours
Week 2	ADP Session # 1	12 hours
	Phone visit #1	10 minutes
Week 3	AABM training session #1 + #2	1.5 hours
	AABM training session #3 + #4	1 hour
	AABM training session #5 + #6	1.5 hours
Week 4	ADP Session #2	12 hours
	Phone visit #2	10 minutes
Week 5	Follow-up visit	30 minutes
TOTAL	12 study visits	approximately 31-32 hours

[^]The amount of time is an approximation

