6.3.5 On study visits

Baseline/screening visit 4 hours	Informed consent + HIPAA Participant Locator form Demographics Eligibility form Medical History Physical Exam Lab tests Height/weight Concomitant Medications Columbian Suicide Severity Rating Scale AE Spontaneous Breath alcohol test Structured Clinical Interview for DSM-5 (SCID) Timeline Followback (TLFB) Clinical Institute Withdrawal Assessment (CIWA-AD) Urine Drug Screen (UDS) Barratt Impulsiveness Scale (BIS-11) Alcohol Use Disorders Identification Test (AUDIT) Alcohol Purchase Task (APT) Obsessive Compulsive Drinking Scale (OCDS) Vitals Balloon Analogue Risk Task (BART) Delay Discounting (DD) Iowa Gambling Task (IGT) Salience Task
Phone Visits 1 and 2 10 minutes each	AE Spontaneous Timeline Followback (TLFB)
Human Lab Sessions 1 and 2 12 hours each human lab	Weight AE Spontaneous Concomitant Medications Breath alcohol test Timeline Followback (TLFB) Clinical Institute Withdrawal Assessment (CIWA-AD) Urine Drug Screen (UDS) Blood alcohol level (BAL) Vitals Alcohol Urge Questionnaire (AUQ) Biphasic Alcohol Effects Scale (BAES) Balloon Analogue Risk Task (BART) Delay Discounting (DD) Ratings of Drinking Behavior During the Alcohol Self-Administration Period
AABM/Sham Training Sessions 1-6 30 minutes each visit	Concomitant medications AE Spontaneous Breath alcohol test TLFB (Sessions 2, 5, and 8 only) CIWA-AD AABM/Sham training
AABM/Sham Training Sessions 1 and 6 an additional 1.5 hours	Obsessive Compulsive Drinking Scale (OCDS) Alcohol Purchase Task (APT) Iowa Gambling Task (IGT) Delay Discounting (DD) Balloon Analogue Risk Task (BART)

	Barratt Impulsiveness Scale (BIS-11) Stop Signal Task (SST)
Follow-up Visit 1 hour	Breath alcohol test Timeline Followback (TLFB) Concomitant medications AE Spontaneous Medical Management (MM) Participant End of Study Questionnaire

Assessments at Study Entry and During and After Human Lab Sessions

At Entry:

These are adapted from previous/ current clinical studies at the UCSF/SFVAMC Addiction Research Program.

- Demographic data, will be assessed with data on age, race, socioeconomic status, marital status, educational and occupational levels, and significant medical history.

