- A number of safety evaluations are included: Medical history and physical examination; Suicide Risk Assessment: The Columbia Suicide Severity Rating Scale [101]. It is a standard, thorough, frequently used method to screen for suicidal ideation, used by our group in alcohol use disorder clinical trials;
- Clinical Laboratory Tests for Health/Safety Monitoring: Blood samples will be collected for chemistry, liver panel, renal panel and complete blood count (CBC); urine will be collected for urinalysis.
- Structured Clinical Interview for DSM5, (SCID) [96]: the SCID will be used to determine DSM-V diagnosis of current (current year) Alcohol Use Disorder, and the DSM-V current psychiatric diagnoses for anxiety, mood, psychotic, and non-alcohol substance use disorders in order to determine study eligibility.
- Study Physician Review: All health measures, medical history/exams and labs will be reviewed by a study physician to ensure that the subject meets all the eligibility criteria and are ready for randomization
- Alcohol Approach Task (AAT): A way to measure pre-treatment alcohol approach bias tendency. Salience Task: A survey that measures the salience of each stimulus image for participant.

At Entry and at various times throughout the study:

- Clinical Institute Withdrawal Assessment for Alcohol, DSM-IV Version (CIWA-AD): at entry and before each Human Lab Session and at each Follow-up;
- Urine Drug Screen: For opioids, benzodiazepines, cocaine, amphetamines, cannabis, barbiturates: at entry and before each Human Lab Session.
- Breath alcohol concentration (BrAC); at entry and before each Human Lab Session; and during each Human lab Session
- Vital Signs: Temperature, heart rate, and blood pressure will be measured at study entry and multiple times during each Human Lab Session.
- Concomitant Medications Review: at entry and before each Human Lab session: thorough review of all concomitant medications (prescription or over-the-counter) in the past 30 days, as well as those started during the study.
- Concomitant Treatment Log: At Entry and A way to track any type of alcohol treatment at baseline/screening and throughout the study.

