- Adverse Effects: Spontaneous: At Entry and at Human Lab Session 1 and 2; Phone visits 1 and 2; AABM Sessions 1-6; 1-wk FU. This form is designed to collect information about adverse health events. We will ask about emergent AEs, follow-up with AEs reported at previous study visits, and ask if there has been a hospital admission since the last study visit.
- Timeline Followback (TLFB): at study entry, then Human Lab Session 1 and Human Lab Session 2. TLFB will be used to calculate standard drinks consumed per week in the past 30 days prior to consent and at the two Human Lab Sessions, and the 1-week follow-up. The TLFB will be used to determine whether subjects meet minimum alcohol consumption criteria at entry. Other substance use will also be collected by TLFB.
- Barratt Impulsiveness Scale (version 11) (BIS-11) [98]: This provides a trait measure of impulsiveness and will be used to characterize the study cohort at study entry.

At AABM Training Sessions:

- Alcohol Use Disorders Identification Test (AUDIT): The AUDIT [97] is valid and reliable self-report measure of alcohol-related problem severity.
- Obsessive Compulsive Drinking Scale (OCDS): At AABM sessions 1 and 6. A questionnaire that measures cognitive aspects of alcohol craving.

- Alcohol Purchase Task (APT): At AABM sessions 1 and 6. A questionnaire uses hypothetical choices regarding alcohol purchases at varying prices to generate several indices of alcohol-related reinforcement.

At Follow-up visit:

- Motivational Enhancement Therapy: at the follow-up visit, research clinician will provide a motivational enhancement session to encourage the non-treatment seeking participants to consider treatment.

Measures of Alcohol Effects:

- Breath alcohol concentration (BrAlc) [99] *at each visit, and multiple times in ADP Sessions 1 and 2*. BrAlc will be measured at each session to detect recent alcohol use with the *Intoximeters Alco-Sensor IV* instrument.
- Blood Alcohol Levels: Human Lab Sessions 1 and 2 (Table 1): Blood samples will be drawn to measure plasma levels of blood alcohol (BAC) during the priming dose and during the alcohol self-administration paradigm. Blood samples will be stored at -4°C and will be analyzed at the San Francisco VA.

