6.4.3.3 Safety

Descriptive statistics will be used to summarize the data. The SAFTEE will be used to assess adverse effects. Descriptive statistics will be used.

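### Suicidal intent or plan triggers withdrawal during the study, but the only scale that screens for it is scheduled at entry and never repeated

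*Combined protocol and SAP*

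**What the plan says.** Section 3.3.2 has a block on protecting participants against heavier drinking, suicidality and other problems emerging while they are on study. Withdrawal follows if the PI or the DSMB judges that any of several conditions is met. They include a sustained increase in drinking, unacceptable adverse events, a residual category of poor outcomes, and "suicidal ideation consisting of suicidal intent or plan". The one monitoring step listed beside the rule concerns alcohol use.

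In the visit table of section 6.3.5, the baseline/screening row contains "Columbian Suicide Severity Rating Scale AE Spontaneous Breath alcohol test". The text after the table places the Columbia scale in the list of entry assessments and says of it: "It is a standard, thorough, frequently used method to screen for suicidal ideation". It is absent from the separate list of measures taken at entry and repeated later, and from every later row of the table.

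General safeguards continue after screening. The adverse-event form is used at every later contact: "We will ask about emergent AEs, follow-up with AEs reported at previous study visits, and ask if there has been a hospital admission". Under section 6.2.2.1 the study physician "will review each participant's safety at each study visit". Section 6.4.3.3 adds: "The SAFTEE will be used to assess adverse effects". The SAFTEE is in no visit row, however, and its content is not described.

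**The concern.** The protocol names a specific psychiatric state as grounds for withdrawal during the study but schedules nothing after screening that asks about it. The PI or DSMB would have to apply the criterion using whatever happened to surface through a general question about adverse events or a clinician's impression. A man with suicidal intent or a plan may not offer that under a prompt about health events and hospital admission.

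The stakes are participant protection across the weeks that contain the alcohol sessions and the training. There is also a reporting consequence. Section 4.2 makes the safety of the alcohol procedure and of the training part of the primary aims, yet the descriptive safety summary in section 6.4.3.3 could not tell men who were asked and denied suicidal thoughts from men who were never specifically asked. The primary outcome variables in section 5.2.1 (time and retention) do not depend on this point.

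**Working it through.** This is a check of the schedule against the rule. There is no figure in the plan to reproduce.

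**1. Contacts after screening**

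- Training sessions counted singly (visit table, 6.3.5): 2 lab + 2 phone + 6 training + 1 follow-up = 11.
- Training sessions paired (6.3.1, rows such as "AABM training session #1 + #2"): 2 + 2 + 3 + 1 = 8.
- Section 6.3.1 lists the paired rows but totals 12 study visits, which matches 11 + 1 screening visit. Both denominators are therefore carried.
- Contacts after Lab Session 1, the first alcohol session: 1 phone + 6 training + 1 lab + 1 phone + 1 follow-up = 10. With pairing, 1 + 3 + 1 + 1 + 1 = 7.

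**2. Scheduled input for each specific trigger, from the visit table**

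| Trigger in 3.3.2 | Measure | Of 11 | Of 8 |
|---|---|---|---|
| Increased alcohol use | Timeline Followback | 7 | 7 |
| Unacceptable adverse events | Adverse-event form | 11 | 8 |
| Suicidal intent or plan | Columbia scale | 0 | 0 |

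The Timeline Followback count is 2 phone + 2 lab + 2 training + 1 follow-up = 7. The training row reads "TLFB (Sessions 2, 5, and 8 only"; there are only six sessions, so sessions 2 and 5 are counted. They fall in different pairs, so the count stays at 7 of 8.

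**3. Other possible sources**

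- The diagnostic interview (SCID) is at baseline only and serves eligibility.
- The adverse-event form and the physician review are general; neither description mentions suicidality.
- The exclusion criteria in 5.3.2 cover serious mental illness and leave medical contraindications to the physician, but do not mention suicidality. Screening out could not in any case detect a problem that starts later.

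**4. Length of the interval**

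- Section 6.3.1: screening in Week 1, follow-up in Week 5, so about 4 weeks.
- Section 5.1.1: second lab session in Week 5 and follow-up 7 days later (Week 6), so about 5 weeks.

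**5. Burden of a repeat at six contacts**

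- Contacts: 2 lab + 2 phone + 1 training + 1 follow-up = 6.
- Administrations, for the 12 to 15 men in 5.3.1: 6 × 12 = 72 to 6 × 15 = 90.
- Time per man at an assumed 2 to 5 minutes each: 6 × 2 = 12 to 6 × 5 = 30 minutes.
- Share of the stated 31 to 32 hours (1,860 to 1,920 minutes): 12/1,920 = 0.6% to 30/1,860 = 1.6%.
- On a 10-minute phone visit: 2/10 = 20% to 5/10 = 50% longer.

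**The case against.** The best reply is that the rule is opinion-based by design. No score or instrument is attached to it, and the clinical input is scheduled: physician review at each visit, real-time contact about adverse events, weekly safety meetings, and oversight by the DSMB and the Medical Monitor. The residual psychiatric trigger in the same sentence has no dedicated later measure either, so the plan may simply rely on judgment for psychiatric events. The first alcohol session also falls only about a week after the Columbia screen, and the adverse-event form and the SAFTEE are not reproduced, so either might contain a suicidality item.

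Part of this stands. Monitoring is not absent. The documents show only that no suicidality-specific measure is scheduled; they do not show that nobody would ask. The exposure is less for Lab Session 1 than for what follows it. No event rate is given, so the number of cases that could be missed cannot be estimated.

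It does not close the gap. Judgment needs information, and meetings and boards review what has already been collected. A catch-all clause naturally has no measure of its own; a specifically named criterion should. The SAFTEE cannot be credited when it is in no visit row and its content is not given.

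A second objection is that Phone Visit 2 and the follow-up come when little or nothing remains to withdraw from, and that a few minutes is a large addition to a 10-minute call. Both are true. Asking there still serves the protective purpose stated in 3.3.2, because those contacts follow the second alcohol session, but the case is stronger for the earlier contacts.

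**Conclusion.** The concern holds, as an inexpensive improvement to participant safety. Suicidal intent or plan is a named reason for withdrawal during the study, and its specific measure is scheduled at 0 of 11 later contacts (0 of 8 paired), including 0 of the 10 (or 7) that follow the first alcohol session. The other two specific triggers have scheduled inputs at 7 or more contacts.

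The counts rest on the visit table as written and on taking the adverse-event form to be the general enquiry described. If that form or the SAFTEE contains a direct suicidality question asked at the later visits, stating so in the protocol would largely resolve the point. The burden figures rest on the assumed 2 to 5 minutes per administration. Nothing inferential is affected, since the plan is descriptive only.

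**What to change.** Add a brief repeat of the Columbia scale to the section 6.3.5 rows for Human Lab Sessions 1 and 2 (before alcohol), Phone Visits 1 and 2, at least one training visit, and the follow-up visit. As a minimum, add one direct question on suicidal thoughts, intent and plan to the adverse-event form at those contacts; this may suit the phone visits best. Send any positive answer through the real-time physician contact already set out in section 6.2.2.1, and add a descriptive summary of the responses to section 6.4.3.3. The withdrawal criterion itself does not change.

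The cost is a protocol amendment and a few minutes at each of six existing contacts, using an instrument already administered at screening. No extra visits or staff are needed. The drawback is slightly more participant burden, felt mainly on the short phone calls.

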****Protection against blood drawing (venipuncture) risks****

To protect against this risk, we will do the following:

- 1) Professionally trained phlebotomists at the CTSI Clinical laboratory will perform all phlebotomies.

Risk of Privacy/Confidentiality

Participation in the study presents a risk to the participant of loss of privacy and confidentiality regarding research material, particularly with respect to potentially embarrassing or harmful personal health information, particularly related to mental health and alcohol and substance use. This includes detailed and sensitive information regarding alcohol and drug use, and psychiatric symptoms. For example, urine drug testing will be conducted. Potential release of information regarding drug use, in particular, could have serious implications if made known, for example legal ramifications, jeopardizing insurability or employability.

In order to ensure the safety of the participant and others, information may be shared between research staff and the clinical team only under the following circumstances: 1) If in the judgment of the study physician, the participant has a psychiatric or medical condition that requires urgent attention to protect the safety of the participant or others; and 2) If a participant has missed several study appointments, and research staff needs to verify the participant's whereabouts and/or verify the participant's safety. These above circumstances will be clearly outlined in the informed consent form, and be discussed and clarified with prospective participants at the start of the study.

****Protection against risks to privacy/confidentiality****

To protect against this risk, we will do the following:

- In the informed consent form, participants are instructed: "Participation in research may involve a loss of privacy, but information about you will be handled as confidentially as possible. If you do not already have a medical record at the VA Medical Center, San Francisco, one will be created because of your participation in this study."
- *HIPAA regulations will be followed throughout this study. Several methods will be used to decrease the risk of loss of confidentiality to participants.*
 - First, all study forms will be labeled with a unique, identifying code number, and maintained in a locked cabinet. Those

that contain the names of participants or other identifying information will be stored in a locked cabinet, separate from other study forms.

o Second, research material will not be shared between the research team and clinical staff - with the exception of information to be shared only to ensure the safety of the participant and others.

o Third, no names will be used in any published reports about this study.

o Fourth, most of the questionnaire data will be collected using an online survey instrument called Qualtrics:

All collected research data will be referenced by unique study identification codes only, stored in an electronic database (SQL server) on a password-protected secure VA server behind a secure VA firewall at SFVAMC available to study staff only. After receiving CHR and R&D approval, we will be collecting most of our questionnaire measures in digital format, so that this questionnaire data can be collected using an online survey instrument called Qualtrics, which meets strict IRB and HIPAA data security requirements. Data will be entered into SQL Server tables using MS Access as a front-end or batch load from an external file. At a point of entry, form values are subjected to consistency edit checks (e.g. range and type verification, missing data). Scoring algorithms are applied where appropriate. Once data is entered into the database, edit checks are run for accuracy.

Unknown Risks

Participants may experience side effects that are not known yet.

